4.2.2 Primary Safety Endpoint

Safety: Incidence, severity and seriousness of device-related Adverse Events.

4.2.3 Secondary Endpoints

- 1. Time to control hemorrhage, defined as the time from turning on the vacuum source until the time the *first* of any of the following occurs:
 - there is no blood being collected in the tubing or canister, or
 - the blood loss is observed as leveled off in the canister, or
 - blood loss is at a rate of < 500 ml in 24 hours.
- 2. Rate of surgical intervention required to control PPH after Jada use.
- 3. Rate of non-surgical intervention required to control PPH after Jada use.
- 4. Assessment of device usability as reported by the clinician using a dedicated data collection form.
- 5. Rate of blood product transfusion required after Jada use, and number of transfusion units when administered.

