6.5 Intervention

The Investigator will use Jada in conjunction with the device's Instructions for Use that is included with every device. Following the steps of the IFU and according to their training, the Investigator will place the Jada intrauterine loop into the uterus. For vaginal deliveries, the device will be placed transvaginally; for Cesarean deliveries, the device will be placed trans-abdominally or transvaginally (if the hysterotomy was closed first). The vacuum seal will be filled with 60 ml sterile IV fluid. Vacuum forces will be applied to suction residual blood and debris. Once the residual blood is removed, the pressure gradient from the vacuum creates a uniform mechanical stimulus on the uterus, causing it to collapse into and onto itself. At that time, tamponade occurs and hemorrhage is expected to be controlled. Vacuum forces will be maintained for at least one hour (from the time hemorrhage is controlled) until the subject is stable or until the Investigator determines that hemorrhage was not

PEARLE Study CIP-01 v2.6 controlled and further intervention is needed. If any further intervention is required to treat the PPH, it will be reported on the Procedure case report form, capturing details on the intervention.

Once the Investigator detaches the tubing from the device or "zero's" the vacuum source and the seal is emptied of the fluid, the device should remain in place and taped to the patient's inner thigh for at least 30 minutes, provided the subject is stable and there is no medically valid reason to remove the device. The 30-minute minimum observation period allows for the Investigator to re-initiate treatment should the uterus return to an atonic state with abnormal bleeding.

If the subject remains stable and the PPH does not return for 30 minutes, then the device can be removed and decommissioned (cut up) prior to final disposal. Device pieces should be discarded in accordance with hospital biohazardous waste policies. If there was a device malfunction, the Investigator or designee should wrap the device in a biohazardous disposal bag and contact Alydia Health for further instructions to return the device for evaluation.

Other standard of care medical evaluation and care must be ongoing during the use of the Jada System. If it is determined that blood products must be administered, then the Investigator should follow the local protocol to do so.

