9.5 Secondary Endpoints

- 1. Time to control hemorrhage, defined as the time from turning on the vacuum source until the time the *first* of any of the following occurs:
 - there is no blood being collected in the tubing or canister, or
 - the blood loss is observed as leveled off in the canister, or
 - blood loss at a rate of < 500 ml in 24 hours.
- 2. Rate of surgical intervention required to control PPH after Jada use.
- 3. Rate of non-surgical intervention required to control PPH after Jada use.
- 4. Assessment of device usability as reported by the clinician using a dedicated data collection form.
- 5. Rate of blood product transfusion required after Jada use, and number of transfusion units when administered.

The secondary endpoints will be summarized, and confidence intervals will be provided to support interpretation of the results. No specific hypothesis tests will be performed for the secondary endpoints.

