9.12 Dropout Mechanism and Analysis

Subjects who are missing data necessary to assess Treatment Success will be considered a failure (Treatment Success = No) in the analysis of the primary effectiveness endpoint. If the subject withdraws from the study prior to completing the assessment of Treatment Success, it will be considered missing data. All other endpoints will be analyzed "as-is" without any special data imputation methods used to replace missing data.

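### Time to control hemorrhage stops at the first sign, which need not last and is not cancelled by later rescue, so a treatment failure can carry a short control time

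*Combined protocol and SAP*

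**What the plan says.** Section 4.2.3 lists time to control hemorrhage as the first secondary endpoint, "defined as the time from turning on the vacuum source until the time the" first of three signs appears:

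- "there is no blood being collected in the tubing or canister";
- "the blood loss is observed as leveled off in the canister";
- "blood loss is at a rate of < 500 ml in 24 hours".

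Section 9.5 repeats the definition, with the third sign worded as "blood loss at a rate of < 500 ml in 24 hours". Neither section gives a minimum duration, a confirming reading, or a rule that withdraws the time if bleeding returns or rescue follows.

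Section 4.2.1 (repeated in 9.3) defines control of hemorrhage for the primary endpoint as getting through without a balloon, packing, embolization or surgery after device use. Secondary endpoints 2 and 3 count the same surgical and non-surgical interventions as rates.

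Section 6.5 keeps the vacuum on for at least an hour counted from control, then leaves the device in place for at least 30 minutes. That second period "allows for the Investigator to re-initiate treatment should the uterus return to an atonic state with abnormal bleeding". Neither period is linked to the time-to-control definition.

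On analysis, section 9.5 provides summaries and confidence intervals: "No specific hypothesis tests will be performed for the secondary endpoints". Section 9.12 analyses all endpoints other than the primary "without any special data imputation methods used to replace missing data". No censoring or competing-event rule is given.

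**The concern.** The plan uses the word control in two ways that can disagree in the same woman. For the primary endpoint, control means that no further intervention was needed. For the time endpoint, it means that a sign was seen once. A woman can therefore be controlled at a few minutes and also be a failure of control.

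This is a stated rule, not a missing detail, and its effect has one direction. A woman who was rescued contributes either a finite time, if she paused, or nothing, if she never met a sign. Neither makes the summary reflect that her bleeding was not controlled.

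At stake is the trial's direct measure of speed. Section 3.7 names more rapid control as a potential benefit, and section 3.5 reports control within two minutes for all ten feasibility subjects. With a single arm, no concurrent comparison would expose times that are too short.

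**Working it through.** The plan states no target, expected value or sample size for time to control, so there is no plan figure to reproduce. The check has two parts.

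**1. One woman under both definitions (hypothetical).** Flow into the canister stops at 2 minutes, resumes at 10 minutes, and a balloon is then placed.

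| Endpoint | Section | Result |
|---|---|---|
| Time to control | 4.2.3, 9.5 | 2 minutes, valid and final |
| Primary effectiveness | 4.2.1, 9.3 | Failure |
| Non-surgical intervention rate | 4.2.3, item 3 | Counted |

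Nothing in sections 4.2.3, 6.5, 9.5 or 9.12 removes the 2 minutes.

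**2. Size.** Inputs from section 5.4.1: 96 evaluable women, expected success 0.82, literature lower bound 0.734. All primary failures are taken to be escalations, and all other women are taken to have a control time.

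Expected number escalating:

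- at 82%: 0.18 × 96 = 17.3, about 17, leaving 79;
- at 73.4%: 0.266 × 96 = 25.5, about 26.

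The number who first met a sign is not given. It lies between 0 and 17 (or 0 and 26).

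Let F be the percentile, among women who did not escalate, at which the overall median falls.

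- *Escalated women counted as never controlled and kept in the denominator:* 0.82 × F = 0.50, so F = 0.50/0.82 = 0.61. At 73.4%, F = 0.50/0.734 = 0.68.
- *Plan as written, no escalated woman met a sign:* they have no time and drop out, so F = 0.50.
- *Plan as written, all escalated women met a sign, each earlier than the median of the others:* 0.18 + 0.82 × F = 0.50, so F = 0.32/0.82 = 0.39. At 73.4%, F = 0.234/0.734 = 0.32.
- *Plan as written, all met a sign, each later than that median:* F = 0.61, the same as when they count as never controlled.

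At 82% success the plan's median therefore falls between the 39th and the 61st percentile of times among the women who did not escalate, depending on data the documents do not contain. Counting escalated women as not controlled puts it at the 61st. The plan's median can equal that value or fall below it, but cannot exceed it. These percentiles do not depend on cohort size. They cannot be turned into minutes, because no distribution of times is given.

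**The case against.** The best defence is that this endpoint measures onset. Time to first control and avoidance of escalation are different questions, and early control followed by failure is a coherent result. Escalation is already counted in the primary endpoint and in secondary endpoints 2 and 3. The time endpoint has no test, comparator or target. All of this stands, and it limits the consequence. It does not justify calling the quantity time to control, without qualification, in a plan that elsewhere defines control as avoiding rescue.

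Four stronger readings are tempting, and the documents do not support them.

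- *Every woman who re-bleeds or is rescued scores as rapidly controlled.* She can, but need not. A woman who bleeds without pause until rescue meets no sign and has no time.
- *A woman whose vacuum is re-initiated holds a false time.* Under section 6.5 re-initiation comes in the observation period, normally after at least an hour of vacuum with bleeding controlled. That is recurrence after real control. It should be reported, but the first time is not an error.
- *A lost seal or a blocked device is recorded as success.* This is an inference from signs read in the tubing or canister. Section 3.2 describes a shield against plugging, section 6.5 requires ongoing standard medical evaluation, and section 7.5 requires malfunctions to be documented. The third sign is not confined to the canister. The Instructions for Use and case report forms are not in the documents and may say more.
- *96 of 96 would appear controlled, against 79 of 96 by the primary endpoint.* This is a ceiling on a proportion the plan never reports. It assumes that every escalated woman paused first and that every other woman met a sign.

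**Conclusion.** The point holds for women who meet a sign and later receive a listed intervention. The definition lets them keep a control time that the primary endpoint contradicts. Compared with counting them as not controlled, the error runs only toward faster control.

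At 82% success, 0 to 17 of 96 women are affected. The corrected overall median is about the 61st percentile of times among the rest (about the 68th if success is 73.4%). This rests on the planned success rates, on all primary failures being escalations rather than missing data counted as failure under section 9.12, and on all other women having a recorded time.

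A reader might infer that the trial's conclusion is at risk. It is not: the primary endpoint counts rescue as failure, section 9.4 bases study success on that endpoint alone, and this endpoint is descriptive. The definition should still be corrected, because the bias is built into the rule and is cheap to remove.

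**What to change.** In sections 4.2.3 and 9.5:

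1. Count any woman who later receives a listed non-surgical or surgical intervention as not controlled. Use the same events as the primary endpoint, so that the two cannot disagree.
2. Keep these women in the denominator, with the intervention as a competing event. Report the cumulative incidence of control and the median over all women in the Safety/ITT Cohort. This also gives a place to women who are rescued without ever meeting a sign.
3. Report the plan's present first-of-three time beside it, labelled *time to initial control*, with the number of women whose vacuum was re-initiated for recurrent bleeding.

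Cost: endpoint and SAP wording and a little extra analysis. Section 6.5 already records further interventions on the Procedure case report form. Confirm that re-initiation is captured there too, since the form is not in the documents. Reported times become somewhat longer. Only the derivation changes; care does not.

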4.3 Overall Study Success

A thorough review of all known publications reporting on the use of the Bakri Balloon to treat PPH was performed. A meta-analysis methodology was used to aggregate the studies and provide a numerical estimate of the overall Treatment Success Rate. Based on a random effects model, the estimated pooled proportion of subjects who reached hemostasis (i.e., control of uterine hemorrhaging)

following Bakri Balloon (or equivalent) treatments was 82.0% (95% CI: 73.4% to 89.2%). See the Clinical Evaluation Report (G150265, Attachment H, pages 337-382).

The primary effectiveness objective of this Pivotal Study is to show that the observed Treatment Success Rate is not worse that the rate reported in the literature. The study is considered a success when the lower bound of the two-sided Exact Clopper-Pearson mid-p 95% Confidence Interval for the Study Treatment Success is greater than or equal to 73.4%.

5.0 Study Design

5.1 Overview

This study design is prospective, single-arm, literature-controlled, and multi-center. Since this is a literature-controlled study, meta-analysis methodology was used to establish target endpoints which will demonstrate the safety and effectiveness of the Jada System. See the Clinical Evaluation Report (G150265, Attachment H, pages 337-382).

5.2 Site Selection

The study will be conducted at no less than five and no more than twenty sites, which may include both U.S. and O.U.S sites. Site selection will be conducted in accordance with sponsor Standard Operating Procedures. If O.U.S. sites are enrolled, they will comply with FDA's February 2018 guidance titled "Acceptance of Clinical Data to Support Medical Device Applications and Submissions, Frequently Asked Questions, Guidance for Industry and Food and Drug Administration Staff."

5.3 Study Training

The training program for sites participating in the study will include the following:

- 1. Didactic training;
- 2. Hands-on training;
- 3. Investigator Training Certification Quiz;
- 4. Procedure Guide Poster.

All investigators will be required to undergo both hands-on training and didactic training and successfully pass the Investigator Training Certification Quiz, which will be administered after the training is complete. The trainee will be considered to have passed the Investigator Training Certification Quiz once all questions have been answered correctly, which may involve a retake of the quiz.

Didactic Training

The didactic training will be performed by Alydia Health staff that are qualified to perform the training. The didactic training will be performed either in person or via videoconference.

Hands-On Training

Hands-on training will be provided by qualified persons who are familiar with the Jada System and PPH. Trainees will use demonstration samples of the Jada System in bench models built by Alydia Health to simulate anatomy in both transvaginal placement and transabdominal placement. This clinical experience simulation is intended to ensure operators master the Jada procedural steps prior to live study subject procedures. Trainees will be required to independently and individually demonstrate successful deployment of a minimum of one Jada System in each model before they are approved to use the device. Successful deployment is defined as following all of the procedural steps in

accordance with the Instructions for Use without prompting or correction by the trainer in the transvaginal model, and successfully completing the device positioning steps in the transabdominal model also without prompting or correction by the trainer. This may require more than one deployment attempt.

Procedure Guide Poster

Finally, as a post-training reminder and reference, each site is provided with a Procedure Guide Poster, which serves as a quick reference guide for the procedure.

5.4 Study Population

5.4.1 Number of Subjects and Sample Size Calculation

Up to 107 subjects will be enrolled in the study to ensure that 96 subjects are available for the analysis of the primary effectiveness endpoint. Sites are expected to enroll a minimum of 5 subjects. Site enrollment will be capped at 30% of the total expected enrollment, such that no site will enroll more than 32 subjects.

The study is powered to show that the Treatment Success Rate among the Jada subjects is not inferior to the Treatment Success Rate derived from a meta-analysis performed using all known publications reporting on the use of the Bakri Balloon (and equivalents) to treat PPH.

Based on a random effects model used in the meta-analysis, the estimated pooled proportion of subjects who reached hemostasis (i.e., control of uterine hemorrhaging) following Bakri Balloon treatments was 82.0% (95% CI: 73.4% to 89.2%). See the Clinical Evaluation Report (G150265, Attachment H, pages 337-382).

Non-inferiority will be achieved when the lower bound of the Exact Clopper-Pearson mid-p 95% Confidence Interval for the Study Treatment Success Rate is greater than or equal to the lower bound of the 95% Confidence Interval of the Treatment Success Rate derived in the meta-analysis, or 73.4%. That is:

Statistical Hypothesis: $H_0: \pi_{Jada} \le \pi_{Literature \ CI \ LB} \ vs \ H_1: \pi_{Jada} > \pi_{Literature \ CI \ LB}$

where π_{Jada} is the Treatment Success Rate for Jada treated subjects and $\pi_{Literature\ CI\ LB}$ is the lower bound of the 95% Confidence Interval for the Treatment Success Rate derived from the meta-analysis of the Bakri

Balloon Literature.

Statistical Methodology: Confidence Interval for π_{Jada}

Expected π_{Jada} : 0.82

Half-width of 95% CI: 0.086

Confidence Level: Two-sided 95%

Minimum Sample Size: n = 96 evaluable subjects

Statistical Power: 0.806 that the lower bound will be greater than or equal to 0.734

With 96 evaluable subjects, there is an 80.6% probability that the lower bound of the observed Exact Clopper-Pearson mid-p two-sided 95% confidence interval will be expected to be greater than 0.734 when the Jada Treatment Success is expected to be 82%. (Calculated using SAS v9.4 PROC POWER.)

For safety, with 96 subjects treated with Jada, there is a 95% chance of observing at least one adverse event when the underlying incidence of the event is at least 3.1%.

To account for up to 10% of the subjects withdrawing early or not having data available for the analysis of the primary effectiveness endpoint, a total of 107 subjects will be enrolled.

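### The stated 80.6% power matches the chance of a narrow interval, not of meeting the success rule; power at a true rate of 82% is about 53%

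*Combined protocol and SAP*

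**What the plan says.** Section 5.4.1 sets the sample size with "Minimum Sample Size: n = 96 evaluable subjects". Its inputs are an expected Jada rate of 0.82, "Half-width of 95% CI: 0.086" and a two-sided 95% confidence level. The bar is "the lower bound of the 95% Confidence Interval of the Treatment Success Rate derived in the meta-analysis, or 73.4"%. From these it reports "Statistical Power: 0.806 that the lower bound will be greater than or equal to 0.734". The text below repeats the claim: "With 96 evaluable subjects, there is an 80.6% probability that the lower bound of the observed Exact Clopper-Pearson mid-p two-sided 95% confidence interval" clears 0.734 "when the Jada Treatment Success is expected to be 82"%. The calculation is attributed to SAS PROC POWER, and no code is given.

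Sections 1.0, 4.3 and 9.4 make that same event, a two-sided 95% mid-p lower limit of at least 73.4%, the criterion for study success. The 0.806 is therefore presented as the probability that the trial succeeds if the planning assumption is true.

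**The concern.** The listed half-width, 0.086, is exactly 0.82 − 0.734. Choosing n so that an interval around the expected rate has that half-width puts its lower limit at about 0.734 when the observed rate equals the expected rate. The trial then passes only if the observed rate is at or above roughly its own expectation, which happens about half the time. A power of 0.806 cannot be squared with that.

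At stake is the stated justification for the size of a pivotal study. If the device performs as planned, the trial has close to even odds of missing its primary endpoint, and a miss could be read as device failure when it is a feature of the design.

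**Working it through.** **Inputs** (all from section 5.4.1; success rule also in 9.4): n = 96; assumed true rate p = 0.82; bar 0.734; half-width 0.086; two-sided 95%; stated power 0.806. X is the number of successes, X ~ Binomial(n, p).

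**Step 1. Reproduce the printed 0.806.** Take the plain Clopper-Pearson 95% interval at n = 96 and define half-width = (upper − lower)/2.

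- 75/96: (0.8592 − 0.6853)/2 = 0.0870, which misses 0.086.
- 76/96: (0.8679 − 0.6967)/2 = 0.0856, which meets it.

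In the relevant range the condition is X ≥ 76, and P(X ≥ 76 | 96, 0.82) = 0.8061. This matches the printed figure to three decimals. Scanning n from 80 to 100, n = 96 is the first to reach 0.80 on this criterion (n = 94: 0.760; n = 95: 0.745). The same calculation with the mid-p interval gives 0.9465, so the match is to the plain interval although the text names mid-p.

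**Step 2. Find the cut-off of the actual success rule.** The mid-p lower limit L for x successes solves P(X > x | L) + ½·P(X = x | L) = 0.025.

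| Successes | Observed rate | Mid-p lower limit | At least 0.734? |
|---|---|---|---|
| 76/96 | 79.2% | 0.702 | No |
| 77/96 | 80.2% | 0.713 | No |
| 78/96 | 81.25% | 0.7251 | No |
| 79/96 | 82.3% | 0.7369 | Yes |

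Success needs X ≥ 79.

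**Step 3. Power of the success rule.** P(X ≥ 79 | 96, 0.82) = 0.5346. The type II error is 1 − 0.535 = 0.465, against 1 − 0.806 = 0.194 as stated. The type I error, P(X ≥ 79 | 96, 0.734), is 0.028.

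**Step 4. Account for the difference.** 0.8061 − 0.5346 = 0.2715, which is exactly P(X = 76) + P(X = 77) + P(X = 78) = 0.0776 + 0.0919 + 0.1020. The printed figure counts three failing results as successes.

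**Step 5. Check other readings.** Each value below is the probability of passing at a true rate of 0.82.

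| Reading | n = 96 | n = 107 |
|---|---|---|
| Mid-p 95%, Wilson 95% or Jeffreys 95% | 0.535 | 0.535 |
| Clopper-Pearson 95% | 0.429 | 0.535 |
| Agresti-Coull 95% | 0.429 | 0.535 |
| Wald 95% | 0.637 | 0.632 |
| Any of these at 90% | 0.637 to 0.728 | 0.632 to 0.720 |
| Normal approximation, one-sided 5% | 0.618 or 0.708 | 0.664 or 0.749 |

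The last row uses the null or the alternative variance. None of these readings comes within 2 points of 0.806.

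**Step 6. What 80% power would take.** At n = 96, P(X ≥ 79) by true rate:

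| True rate | 82% | 84% | 85% | 86% | 88% | 90% |
|---|---|---|---|---|---|---|
| Power | 0.535 | 0.731 | 0.814 | 0.882 | 0.964 | 0.994 |

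Power equals 0.80 at a true rate of about 84.8%. With the true rate held at 82%, mid-p power first reaches 80% at n = 183 (0.811). Exact power is not monotone in n, and it stays at or above 80% only from n = 196 (scanned to 299).

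**The case against.** Four points can be made for the plan.

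- **The origin of 0.806 is inferred.** The documents contain no PROC POWER code, so the half-width explanation rests on the numerical match, the listed 0.086 input and n = 96 being the first n to qualify. That is strong evidence but not proof. The 53.5% does not depend on it.
- **Jada may do better than 82%.** Sections 3.5 and 5.6 report bleeding controlled in all ten feasibility subjects, and at 85% the trial does have about 81% power. This limits the practical consequence. However, section 5.4.1 attaches its 80.6% to 82%, and names no higher planning rate.
- **The conclusion drawn from the data is unaffected.** This stands. The hypothesis, the success rule and its type I error are untouched; the error raises the risk of a failed trial, not of a false claim of effectiveness.
- **The trial enrols 107, not 96.** Analysing 107 does not help: the cut-off becomes 88/107 and power is again 0.535. That value also assumes no missing outcomes. Section 9.12 counts missing outcomes as failures and section 9.6 judges success on the Safety/ITT cohort. If 107 were treated and 5 outcomes were missing, P(X ≥ 88 | 102, 0.82) is about 0.16. Few in-hospital outcomes may be missing, and not everyone enrolled need be treated, so this is an illustration only.

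The sentence's loose wording about what is expected is no defence, because the separate power line is unambiguous.

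**Conclusion.** The concern holds. On the plan's own inputs (n = 96, true rate 82%, mid-p two-sided 95% lower limit of at least 73.4%) power is 53.5%, not 80.6%. Reading the rule as plain Clopper-Pearson gives 42.9% (cut-off 80/96), which is a sensitivity figure because the rule names mid-p. The result assumes independent binomial outcomes with a common success rate and no missing outcomes among the 96. It is specific to a true rate of 82%. Nothing elsewhere in the documents corrects or explains the printed figure.

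**What to change.** Rewrite the power statement in section 5.4.1 to say that:

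- with 96 evaluable subjects, success requires at least 79 successes;
- power is about 53% at a true rate of 82%;
- 80% power is reached only if the true rate is about 84.8% or more.

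Add the power table by true rate from step 6. Remove the half-width as the basis for power; if it is kept, label it as precision and name the interval it was computed with.

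The sponsor should also record which position it takes: that it accepts about 53% power at 82%, that it plans on a higher rate with reasons, or that it reconsiders n.

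The correction costs protocol and SAP wording only. It requires no additional subjects and no change to the endpoint, the success rule or conduct. The price is a less favourable stated power.
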